⁴ Lipid profile includes: TC, LDL-C, HDL-C, TG

⁵ Hematology includes: platelet count, hemoglobin, hematocrit, RBC, WBC with differential

⁶ Chemistry includes: albumin, blood urea nitrogen, creatine kinase, serum creatinine, fasting glucose, calcium, phosphate, potassium, sodium, total protein

⁷ Including urine HCG at screening for subjects of childbearing potential. Dipstick tests performed and results maintained at investigational sites.

⁸ Hepatitis Serology: hepatitis A (IgM), B by HBs-Ag, Anti-HBs, Anti-HBc , C (HCV)

⁹ Liver Safety Panel: ALT (SGPT), AST (SGOT), GGT, ALP, bilirubin (direct and total)

¹⁰ Additional biomarker laboratory test samples will be collected on a selected subset of subjects

¹¹ Lipoproteins include: apoA-I and apoB

¹²Inflammation Panel includes: hsCRP, fibrinogen, and inflammatory cytokines

¹³ Serum/plasma samples for future biomarker analysis in lipid/inflammation

¹⁴ Optional: whole blood will be collected for DNA analysis (Visit 2 only) and mRNA analysis (both Visit 2 and 5) if consent obtained.

¹⁵ Montreal Cognitive Assessment (MOCA) will be performed on subjects ≥70 years of age at randomization

¹⁶ Only statin will be dispensed at screening visit and LVT.

List of Abbreviations

ACS	Acute Coronary Syndrome
AE	Adverse Event
AESI	Adverse Event of Special Interest
ALP	Alkaline Phosphatase
ALT	Alanine Aminotransferase
ANCOVA	Analysis of Covariance
apoA-I	Apolipoprotein A-I
apoB	Apolipoprotein B
API	active pharmaceutical ingredient
AST	Aspartate Aminotransferase
ASSERT	apoA-I Synthesis Stimulation Evaluation in Patients Requiring Treatment for Coronary Artery Disease
ASSURE	ApoA-I Synthesis Stimulation and Intravascular Ultrasound for Coronary Atheroma Regression Evaluation
AUC	Area under time curve
BET	Bromodomain and Extraterminal
BID	twice daily
BMI	Body Mass Index
BRD	Bromodomain
BRD4	BET protein 4
CABG	Coronary Artery Bypass Grafting
CAD	Coronary Artery Disease
CEC	Clinical Events Committee
CI	Confidence Interval
CK	Creatine Kinase
CRO	Contract Research Organization

CSC	Clinical Steering Committee
CV	Cardiovascular
CVD	Cardiovascular disease
CYP7A1	cholesterol 7-alpha hydroxylase
DM	Diabetes Mellitus
DSMB	Data Safety Monitoring Board
ECG	Electrocardiogram
eCRF	Electronic Case Report Form
eGFR	Estimated Glomerular Filtration Rate
EDC	Electronic Data Capture
EQ-5D-5L	EuroQOL five dimensions questionnaire
FAS	Full Analysis Set
FDA	Food and Drug Administration, US
FXR	Farnesoid X Receptor

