6.5 RVX000222 Investigational Drug Administration

RVX000222 or matching placebo will be taken orally with meals in the morning and in the evening, 10-12 hours apart. If a dose is missed, subject should take missed dose at the time it is remembered, unless it is within four hours of the next scheduled dose. If within four hours of the next scheduled dose, missed dose should be skipped. Subjects will take their first dose of investigational drug while in clinic during Visit 2.

Table 3: Investigational Drug Administration Schedule

Treatment Group	Daily dose (mg)	Dose administration b.i.d. (mg)	AM Dose (mg)	PM Dose (mg)	No. of capsules/day
A: RVX000222	200	100	100	100	2
B: Placebo	0	0	0	0	2

If subjects have elevated ALT values (see Section 6.10.1) they may be administered investigational drug or matching placebo at a reduced dose of 50 mg b.i.d, subject to confirmation by the medical monitor.

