7.2.1 Screening/ Study Visit 1 (Week -2 to -1)

Before any study-specific procedures are performed, the subject must receive an explanation of all study procedures, have an opportunity to ask questions, and must sign and date an Institutional Ethics Committee (IEC) approved written informed consent form.

The following will be conducted at Screening:

- Assess inclusion/exclusion criteria
- Document in the subject's medical records the participation in this clinical trial, that informed consent has been obtained, and that a copy of the signed informed consent form has been given to the subject.
- Prepare subjects for the first treatment period participation by informing them of study restrictions and study procedures
- Record demographics
- Measure height and weight
- Review and record complete medical history (including CV history)
- Record prior and concomitant medications (including all CV medications), including detailed information related to the dose, starting and end dates for all medications. Prior medications taken during the 30 day period before Visit 1 will be collected
- Measure vital signs
- Perform a physical examination
- Perform a standard 12-lead ECG
- Collect clinical laboratory samples: fasting lipid profile, hematology, HbA1c, chemistry, urinalysis, liver safety panel
- Perform serology for hepatitis A, B, and C viruses
- Perform urine pregnancy test (female subjects of childbearing potential only)
- Subjects will continue or begin high intensity statin therapy as described in Section 6.6.

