7.2.2 Study Visit 2/Randomization (Week 0)

- Review inclusion and exclusion criteria
- Record any AEs
- Record concomitant medications
- If subject satisfies all inclusion and exclusion criteria, randomization may occur
- Measure vital signs
- Collect clinical laboratory test samples: liver safety panel
- Collect biomarker laboratory test samples in a selected subset of subjects: lipoproteins, fasting insulin, and inflammation panel
- Collect serum/plasma archive samples
- Collect blood samples for pharmacogenomic testing (DNA and RNA) if subject consent received
- Perform MOCA test for any subjects ≥ 70 years of age at randomization
- Administer EQ-5D-5L
- Dispense investigational drug
- Dispense high intensity statin

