9.7 Safety Analysis

Drug administration, disposition data, medical history and prior medications will be summarized by treatment group using descriptive statistics. Safety data such as clinical laboratory results, vital signs, findings from physical examinations, and MOCAs will be listed and summarized by treatment group where appropriate. For continuous variables, these summaries will include sample size, mean, median, standard deviation, minimum, and maximum. For categorical variables, these summaries will include frequencies and corresponding percentages. No inferential hypothesis testing will be performed on the safety variables.

The assessment of safety will be based on the frequency, intensity, and types of AEs and for change and shift from Baseline in the clinical laboratory variables, and vital sign measurements. Baseline values for clinical laboratory variables, and vital sign measurements are defined as the last non-missing values obtained prior to dosing. Clinical laboratory variables outside reference ranges will be flagged in clinical laboratory listings.

Adverse events will be summarized using the safety set. Adverse events will be coded using MedDRA (version 17.0 or higher), summarized by frequency, severity, relationship to study drug, and number of subjects per treatment and by the preferred term and system organ class. Data will be summarized using preferred term and primary system organ class. The coded events will be summarized by treatment group, in subsets of all treatment-emergent AEs, all treatment-related AEs, non-serious treatment emergent AEs and serious treatment emergent AEs. Adverse events of special interest (opportunistic infections and all serious/severe infections) will be analyzed as a subset of the overall AEs. Treatment-emergent AEs will be defined as any AEs, regardless of relationship to study drug, that occur after the first dose of double-blind investigational drug and within 14 days after the last dose of double-blind investigational drug. Treatment-related AEs will be defined as any AEs that are considered by the investigator to be either possibly, probably, or definitely related to study drug. In addition, if relationship information is missing, the AE will be considered treatment-related. Listings for the subsets of SAEs and treatment-related SAEs will be provided.

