4.5. Definition of Time Points, Study Dates, Visit Windows, and Duration

Study Day 1 is defined as the day of randomization when subjects will receive the first dose. Other study days are defined relative to Study Day 1, e.g. the day prior to Study Day 1 is Day -1 and the day after Study Day 1 is Day 2. Study days will not be computed for subjects who are not randomized.

All scheduled study visits will be defined relative to Study Day 1. For example, the appropriate day for the scheduled Week 2 visit should be: Day 1 + 14 = Day 15. A windowing convention which will be used to determine the analysis value for a given study visit will be applicable for all by-visit summaries and analyses. The study visit window can be found in the “Schedule of Events” in the study protocol and also presented in the following table below:

Table 1: Visit Windows for Efficacy and Safety Variables

Study Week	Scheduled Day	Study Day Range
0	Baseline (Day 1)	<=1
2	15	12 18
4	29	26 32
6	43	40 46
8	57	54 60
10	71	68 74
12	85	82 88
16	113	110 116
20	141	138 144
24	169	166 172
28	197	194 200
40*	281	274 288
52	365	358 372
64	449	442 456
76	533	526 540
88	617	610 624
100	701	694 708
112	785	778 792

*Visits to occur with +/- 7-day window past week 40 every 12 weeks

Study treatment will be terminated in all currently participating subjects when the 250th event occurs and all surviving patients have been followed for at least 24 weeks from randomization. At that time all subjects actively treated will conduct their Last Visit on Treatment. Follow up visit is to be scheduled 4 weeks after last visit on treatment. Last visit on treatment and follow up are subject to +/-7 day window.

The baseline value for a variable is defined as the last observation collected on or before Study Day 1/first dose date & time; it cannot be substituted for any post-baseline value. Unscheduled visits or Study visits that are outside the protocol defined windows will be mapped to the closest study visits. All safety data with incomplete dates will be forwarded to Data Management for query.

One or more results for a particular variable may be obtained in the same visit window due to unscheduled or repeated measurements. In such events, the result with the date closest to the expected visit date (scheduled day) will be used. In the event that 2 observations equidistant from the expected visit date are available, the later observation will be used.

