Subgroup analyses will be conducted for the primary endpoint based on the following categorizations:

- Subjects receiving rosuvastatin and those receiving atorvastatin
- Index acute coronary syndrome ≤ 30 days and > 30 days pre randomization
- LDL/HDL/TG’s above and below median value for the study sample
- HbA1c above and below median value for the study sample
- GFR ≥ 60 mL/min and < 60 mL/min as calculated at baseline
- hs-CRP \geq and below the median, as collected at Visit 2
- ALP above and below median as collected at screening,
- Males and Females

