8.4. Other Secondary and Exploratory Analysis

Other secondary and exploratory endpoints are listed in [sections 3.2.2.1](#) and [3.2.3](#). Quantitative endpoints that are defined as a (percent) change from baseline will be analyzed using analysis of covariance (ANCOVA) models with treatment group, baseline value, and strata as covariates. Descriptive statistics for (percent) change from baseline at each post-baseline visit will be summarized using the FAS.

Descriptive statistics (number of subjects with non-missing values, mean, standard deviation, minimum, 25th percentile, median, 75th percentile, and maximum) will be used to summarize continuous variables by treatment group for the FAS set.

Least squares (LS) means and difference in LS means between RVX000222 and Placebo with standard errors (SEs) and 2-sided 95% CI and p-values obtained from ANCOVA model will be presented at each applicable post baseline visit.

Mixed-effects model repeated measures analysis will be used to model percent change in measurements over time at the last visit on treatment (LVT). An unstructured covariance matrix will be used to fit the underlying MMRM model. Subject and error will be considered random effects; all effects that include treatment, strata and baseline value will be considered fixed.

The pattern of change from baseline over time will also be displayed graphically in Figures for some endpoints. No multiplicity adjustment is planned to test the other secondary and exploratory endpoints. Since most of the other secondary endpoints are clinical laboratory tests, they are also summarized under safety analysis in [section 9](#).

Analyses will summarize EQ-5D-5L scale and subscale scores at each visit and change from baseline at each visit.

Analyses will address mean differences by treatment group on MOCA scale and differences for subjects with a baseline score indicative of cognitive impairment (Baseline MoCA < 26)

9. Safety Analysis

Safety data such as clinical laboratory results, vital signs, findings from physical examinations will be listed and/or summarized by treatment group where appropriate. No inferential hypothesis testing will be performed on the safety variables.

The assessment of safety will be based on the frequency, intensity, and types of AEs and for change and from Baseline in the clinical laboratory variables, and vital sign measurements.

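### ALP is read twice before dosing in every subject, but the SAP uses one reading at a time, and a different one for the ALP subgroup than for the ALP baseline and quartiles

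*SAP*

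**What the plan says.** **Two pre-dose readings.** Protocol 7.2.1 (Visit 1, one to two weeks before randomization) lists: "Collect clinical laboratory samples: fasting lipid profile, hematology, HbA1c, chemistry, urinalysis, liver safety panel". Protocol 7.2.2 (Visit 2, Week 0) lists: "Collect clinical laboratory test samples: liver safety panel". Neither item is limited to the biomarker subset. The footnote to the Schedule of Events shows that the panel contains ALP: "Liver Safety Panel: ALT (SGPT), AST (SGOT), GGT, ALP, bilirubin (direct and total". On dosing, Protocol 6.5 says: "Subjects will take their first dose of investigational drug while in clinic during Visit 2". The Visit 1 sample is therefore pre-dose, and so is the Visit 2 sample if it is drawn before the in-clinic dose.

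**Baseline rule.** SAP 4.5: "The baseline value for a variable is defined as the last observation collected on or before Study Day 1". Protocol 9.7 agrees: "Baseline values for clinical laboratory variables, and vital sign measurements are defined as the last non-missing values obtained prior to dosing". For ALP this means Visit 2, with Visit 1 used only if Visit 2 is missing.

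**Where each reading is used.** SAP 8.4 analyses change from baseline with "analysis of covariance (ANCOVA) models with treatment group, baseline value, and strata as covariates", and its MMRM also carries a single baseline value. SAP 3.2.2.1 lists ALP change overall and by baseline quartile, so the quartiles follow Visit 2. The primary-endpoint subgroup in SAP 8.2 is "ALP above and below median as collected at screening", which is Visit 1. No section uses both readings or explains why the subgroup departs from the baseline definition.

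**The concern.** A single ALP value carries day-to-day and assay variation. If the earlier reading says something about a subject's usual level that Visit 2 does not, leaving it out of the model widens the interval for the RVX000222–placebo difference in ALP change, overall and within quartiles. A split on one noisy reading also puts more subjects in the wrong half, which dilutes any real difference in the MACE effect by ALP.

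There is also an inconsistency. The quartile results for ALP change and the median-split results for MACE would be read side by side as low-ALP and high-ALP groups, yet they sort subjects on different samples.

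**Working it through.** **The plan's own figure.** The documents give no SD, correlation or power for ALP. The only power figure is about 80% for the primary endpoint (250 events, hazard ratio 0.7, two-sided 5%). It reproduces: Φ(|ln 0.7|·√250/2 − 1.96) = Φ(2.82 − 1.96) = 80.5%. Nothing below changes it.

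**ALP change: formula.** Let r1 and r2 be the correlations of the Visit 1 and Visit 2 readings with a follow-up reading, and r12 their correlation with each other. All three are assumed. As a fraction of the follow-up variance, the residual is:

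- Visit 2 only: 1 − r2²
- both as covariates: 1 − (r1² + r2² − 2·r1·r2·r12)/(1 − r12²)

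With Visit 2 in the model, analysing change from Visit 2 or the follow-up value gives the same residual. For percent change the formulas are approximate.

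**ALP change: results.**

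| Assumed structure | r1 | r2 | r12 | Visit 2 only | Both | Cut in variance |
|---|---|---|---|---|---|---|
| All equal | 0.70 | 0.70 | 0.70 | 0.510 | 0.424 | 17% |
| All equal | 0.80 | 0.80 | 0.80 | 0.360 | 0.289 | 20% |
| All equal | 0.90 | 0.90 | 0.90 | 0.190 | 0.147 | 22% |
| Closer to each other than to follow-up | 0.80 | 0.80 | 0.85 | 0.360 | 0.308 | 14% |
| Same | 0.70 | 0.70 | 0.85 | 0.510 | 0.470 | 8% |
| Same | 0.80 | 0.80 | 0.90 | 0.360 | 0.326 | 9% |
| Same | 0.70 | 0.70 | 0.90 | 0.510 | 0.484 | 5% |
| Visit 1 predicts less well | 0.70 | 0.80 | 0.80 | 0.360 | 0.350 | 2.8% |
| Same | 0.70 | 0.80 | 0.85 | 0.360 | 0.359 | 0.4% |
| Serial decay (r1 = r2·r12) | 0.64 | 0.80 | 0.80 | 0.360 | 0.360 | 0% |

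A 20% variance cut is about a 10% smaller standard error (1 − √0.80); a 5% cut is about 2.5%.

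**Why separate covariates and not the mean in the model.** At r1 = 0.70, r2 = r12 = 0.80, the mean of the two readings leaves 1 − 0.75²/0.90 = 0.375. That is 4% worse than Visit 2 alone, whereas separate terms are 2.8% better.

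**Subgroup misclassification.** If the two readings measure one stable level with equal error and correlation ρ (bivariate normal), the share on the wrong side of the median is arccos(√ρ)/π for one reading and arccos(√(2ρ/(1+ρ)))/π for the mean of two.

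| ρ | One reading | Mean of two | Visit 1 and Visit 2 halves disagree, arccos(ρ)/π |
|---|---|---|---|
| 0.7 | 18.5% | 13.8% | 25% |
| 0.8 | 14.8% | 10.8% | 20% |
| 0.9 | 10.2% | 7.4% | 14% |

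At ρ = 0.8 this is about 354 against 260 of 2400 subjects. A simulation at ρ = 0.8 gave the same residual variances (0.360 and 0.289) and misclassification (14.8% and 10.8%).

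**How much the ALP test needs this.** Protocol Table 2 gives median ALP changes of −11% and −3.23% (n = 331 and 166, p < 0.001). Treating these roughly as means, the difference is 7.77, the standard error is at most 7.77/3.29 = 2.36, and the SD is at most 2.36/√(1/166 + 1/331) ≈ 25. For an effect of that size, z is at least about 7.7 with 1200 per arm and about 3.8 with 300 per arm (one quartile). The whole-sample test has room to spare; the quartiles have less.

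**The case against.** The strongest reply is that this is a preference and not a defect. The last value before dosing is a clear, prespecified baseline, stated alike in the SAP and the Protocol and applied equally to both arms. That stands. A reader might infer that discarding Visit 1 biases the ALP comparison or makes the baseline rule wrong; nothing in the documents supports that.

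The size is also open to challenge. A reader might take 17–22% as the expected gain. Those figures need a reading one to two weeks before Visit 2 to correlate with it no better than with readings a year or more later, which is the most favourable structure in the table. The documents do not establish it, and under serial decay the gain is zero.

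Exchangeability is doubtful too. Some subjects start or switch statin at Visit 1 (Protocol 6.6), and the index event may be only 7 days before Visit 1 (Protocol 5.2). This limits any averaging for the subgroup. It matters less for the model, where separate coefficients let the data weight the readings. It also bears on the present subgroup rule, which relies on Visit 1 alone.

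Finally, eligibility rests on Visit 1 laboratory results, so Visit 2 ALP is scheduled but is not a condition of randomization. Protocol 9.8 does not impute missing values, and SAP 4.5 does not impute results. Without a stated rule, a model with both terms would drop anyone lacking one reading. That objection stands, and the fix has to answer it.

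**Conclusion.** The point holds as an optional improvement. Two pre-dose ALP readings are scheduled for every subject, each analysis uses one of them, and the subgroup and the quartiles use different ones. Both precede treatment, so using both cannot bias the arm comparison.

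The gain is uncertain because the documents give no ALP correlations. Residual variance falls by about 0% to about 20%, and by 5–14% when the readings correlate 0.85–0.90 with each other and 0.70–0.80 with later visits. The fall in misclassification from about 15% to 11% holds only for exchangeable readings with correlation 0.8.

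A reader might also infer a threat to the trial's main conclusions. The documents do not support that: ALP change is supportive and outside the gate-keeping (SAP 8), the whole-sample ALP test is probably already well powered, and primary power and alpha are unaffected. The benefit is mainly in the ALP quartiles and the ALP subgroup of the primary endpoint. Its effect on the MACE subgroup comparison has not been quantified.

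**What to change.** 1. **SAP 8.4, ALP change.** Keep change measured from the SAP 4.5 baseline. Enter Visit 1 and Visit 2 ALP as separate covariates in the ALP ANCOVA and MMRM.
2. **Missing reading.** State that when one pre-dose reading is missing, the available one is used in its place, so that no subject is dropped. Record this as an explicit exception, for a baseline covariate only, to the no-imputation statements in Protocol 9.8 and SAP 4.5.
3. **SAP 8.2, ALP subgroup.** Replace the screening reading with the same pre-dose ALP definition that is used for the quartiles in SAP 3.2.2.1. The mean of the two readings, or the single one available, is reasonable for both if the readings are roughly exchangeable. Pooled blinded data on the Visit 1–Visit 2 shift and correlation can inform that choice. If exchangeability looks doubtful, one common single-reading definition still removes the inconsistency.

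The cost is one more model term, a missing-reading rule and a few sentences of SAP text, settled before unblinding. No new samples are needed.

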If the CRF dates are needed for variable derivation or calculation and they are missing after querying the sites, the imputation rules below will be employed. However, no results or outcomes will be imputed.

- If the day is missing in the interim data cut, impute missing day as 15th of the month.
- If the month is missing, impute the month as July.
- Additionally, if both day and month are missing, impute to 15JUL.

- If month/year of the onset date is on or after the month/year of Study Day 1, the AE will be considered on-study;
- If month/year of the onset date is equal to the month/year of Study Day 1, and the end date is present, the end date will be used to determine when the AE resolved. If the end date is on or after Study Day 1, the AE will be considered on-study; otherwise, if the AE stopped before Study Day 1, then it will not be on-study; If month/year of the onset date is equal to the month/year of Day 1, and the end date is a partial date, the AE will be considered on-study.

In addition, durations (e.g. treatment duration) will be measured in weeks and will be calculated as:
(End Date – Start Date + 1)/7.

- Intervals that are presented in weeks will be transformed from days to weeks by using (without truncation) the following conversion formula:
WEEKS = DAYS /7.
- Intervals that are presented in months will be transformed from days to months by using (without truncation) the following conversion formula:
MONTHS = DAYS /30.4375.

5. Subject Disposition

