7.2. Prior and Concomitant Medications

Prior and concomitant medications, including antidiabetic medications, will be coded using the latest WHO Drug dictionary Version June, 2010 or higher and classified into the default anatomical therapeutic chemical (ATC) classification system codes provided by the system (the first ATC code by alphabetic order).

Any medication that was stopped prior to the treatment start date will be considered a prior medication. Medication taken at any time between the treatment start date and the date of last contact, inclusive, will be considered concomitant medication. If the medication start or stop dates are missing or partially

missing and the medication is not checked as ongoing, general imputation rules from [section 4.5](#) will be applied. Subject data including prior and concomitant medications including antidiabetic medications will be presented.

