9.1.1. Incidence of Adverse Events

A Treatment-Emergent AE (TEAE) will be defined as any AEs, regardless of relationship to study drug, that occur after the first dose of double-blind study drug and within 14 days after the last dose of double-blind study drug. An AE with a reported onset date after the subject has signed the informed consent document and before the date of randomization (or the date of first dose of study drug if a subject was treated but no randomized) will be considered a pre-study event. AEs with missing onset dates will be considered on-study events.

If the day of onset of an AE is missing, and if the month and year of an onset date are on or after Day 1, general imputation rules from [section 4.5](#) will be applied.

If, despite implementing the above conventions, the onset date of the AE cannot be placed before, on, or after Day 1, then the event will be considered on-study.

All AEs will be coded using the MedDRA Version 17.0 or higher coding system. In this dictionary, each diagnosis is mapped to a lower level term and then to a preferred MedDRA term, which is then mapped to a system organ class.

TEAEs will be summarized by treatment group and overall for the SS. Summaries of TEAEs will be displayed by descending overall frequency for system organ class and preferred term. Treatment-Emergent AEs and SAEs will include events per 100 subject-years of study drug exposure. In addition, TEAEs leading to Study Drug Discontinuation, Serious TEAEs and TEAEs resulting in Deaths will be presented.

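### The partial-date imputation in SAP 4.5 has no bounds, so a medication can stop before it starts and an adverse event in the month of first dose can fall outside the treatment-emergent definition

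*SAP*

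**What the plan says.** SAP 4.5 covers CRF dates that are needed for a derivation and are still missing after query. It has three rules:

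- Day unknown, with a rule worded for one analysis only: "If the day is missing in the interim data cut, impute missing day as 15th of the month"
- Month unknown, with no such limit: "If the month is missing, impute the month as July"
- Only the year known: the date becomes 15 July of that year.

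It limits their scope with "However, no results or outcomes will be imputed". No rule ties an imputed date to first dose, randomization, the start of the same record, last contact, death or the data cut.

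For AEs there are several defaults. SAP 4.5 says "If month/year of the onset date is on or after the month/year of Study Day 1, the AE will be considered on-study", with an exception when a known end date falls before Day 1. SAP 9.1.1 adds "AEs with missing onset dates will be considered on-study events". It sends an onset to the 4.5 rules when the day is missing and the month and year are known and not before Day 1. It closes with a fallback: "If, despite implementing the above conventions, the onset date of the AE cannot be placed before, on, or after Day 1", the event counts as on-study. The same section defines a treatment-emergent AE by date: after first dose and up to 14 days after last dose.

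For medications, the sentence in SAP 7.2 that begins "If the medication start or stop dates are missing or partially" applies the 4.5 rules to both ends of the record unless the drug is marked as ongoing. A drug stopped before treatment start is prior. One taken between treatment start and last contact is concomitant.

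**The concern.** A mid-point convention is harmless while it stays inside what is already known about the record. Without bounds it can contradict the known part of the same record (a stop before a recorded start) or cross the boundary on which a table depends (first dose). The tables at stake are the treatment-emergent AE summaries, including those per 100 subject-years, and the split of medications into prior and concomitant.

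Two wording gaps add to this. The missing-day rule is limited to the interim cut, although SAP 7.2 and 9.1.1 call on the 4.5 rules without that limit. Read literally, a date known to the month has no rule at the final analysis, while a less informative year-only date does. And the SAP does not say whether the 15 July rule or the on-study defaults govern an AE dated only to a year.

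**Working it through.** The plan gives no figure to reproduce here. The check applies the rules as written to example dates (illustrative, not trial data) and then counts cases. The documents do not give the distribution of partial dates, so the counts assume uniform dates over a 365-day year.

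**1. Medication stop (SAP 4.5 and 7.2).** Start 5 September 2016, stop recorded as 2016. The imputed stop is 15 July 2016. Duration by the 4.5 formula is (end - start + 1)/7 = (-52 + 1)/7 = -7.3 weeks. If treatment began after 15 July and by 5 September, the drug was begun on treatment yet meets the prior definition through its imputed stop. Its known start can also meet the concomitant definition, so the two classes collide.

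**2. AE with only the day missing (SAP 4.5 and 9.1.1).** Day 1 is 22 March, onset recorded as March. The imputed onset is 15 March, Day -7. The month/year default keeps it on-study, but the date precedes first dose, so it fails the treatment-emergent definition.

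How often, among AEs that truly start on or after Day 1 in the month of first dose? In a month of n days there are n(n+1)/2 pairs of first-dose day and onset day. The imputed date is too early whenever first dose is after the 15th, which gives (n-15)(n-14)/2 pairs.

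| Month length | Months | All pairs | Too early |
|---|---|---|---|
| 31 | 7 | 7 × 496 = 3472 | 7 × 136 = 952 |
| 30 | 4 | 4 × 465 = 1860 | 4 × 120 = 480 |
| 28 | 1 | 406 | 91 |
| Total | 12 | 5738 | 1523 |

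1523/5738 = 26.5%, about 27%. For a given subject it is none if first dose is on or before the 15th and all if it is later. These are cases where the 15th is actually imputed: at the interim as worded, and at the final analysis if the cross-references are taken to extend the rule.

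**3. AE dated only to the year.** Day 1 is 10 October 2016, true onset 20 November 2016 (Day 42). The 15 July rule would give Day -87, and July is before October, so the month/year default does not help. There are two readings:

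- *The 9.1.1 defaults govern.* A year-only onset does not meet the 9.1.1 condition for using the 4.5 rules, so it is missing or unplaceable and stays on-study. Share misplaced: 0%.
- *The general rule governs.* Every same-year onset in a subject first dosed after 15 July is dated before Day 1. All same-year pairs: 365 × 366/2 = 66795. First dose after 15 July (169 days): 169 × 170/2 = 14365. Share: 14365/66795 = 21.5%. If the month/year default is also applied to the imputed month, first doses on 16 to 31 July are rescued, leaving 153 × 154/2 = 11781, or 17.6%.

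**4. Effect of bounding.** The medication stop moves to 5 September 2016, the March onset to 22 March and the year-only onset to Day 1. Power, event count and sample size are not involved.

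**The case against.** The strongest reply is that the SAP already protects AEs. SAP 9.1.1 is the specific section, it uses the general rules only when month and year are known, and its fallback would have little left to do if 15 July placed every year-only onset. That is a good argument for the 0% reading. It does not settle the matter, because the precedence is not written down. It also does not touch the missing-day case, where on-study status is protected but the date-based treatment-emergent definition is not.

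A second reply is that such dates will be rare. SAP 4.5 sends incomplete safety dates for query. A same-year onset after a first dose later than 15 July falls by Day 169 at the latest, when visits are 2 to 4 weeks apart and AEs are recorded at each. Protocol 9.1 adds a blinded data review before unblinding. Safety variables have no hypothesis tests (SAP 9), and calendar-driven misdating under blinded 1:1 allocation has no reason to favour an arm. All of this stands and limits the size of the problem.

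A reader might infer two stronger things. The first is that on-treatment AEs simply become pre-study. The on-study defaults prevent that for onsets with a known month, and for year-only onsets it depends on the unstated precedence. The second is that primary event times can be negative. The documents do not show this: the rule covers CRF dates, SAP 4.5 disclaims imputing outcomes, SAP 4.1 lists adjudication data as a separate source, and SAP 8.1 and 8.2 take the confirmed event from adjudication. Partial death and last-contact dates are not expressly excluded, but that is a gap in wording and not a demonstrated consequence.

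**Conclusion.** The point holds as a minor one. Followed as written, the rule produces impossible medication records, and it can date an on-study AE before first dose. The missing-day rule is limited to the interim without a stated reason.

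About 27% of day-missing onsets in the month of first dose would be dated too early. For year-only onsets the share is 0% or about 21.5% of same-year post-dose onsets, according to the reading. These shares assume uniform first-dose and onset dates. The documents give uniform accrual over 1.7 years, which is not a whole number of calendar years, so the calendar spread is itself an assumption. They are shares of partial dates only, whose number is unknown and probably small. The effect is confined to descriptive safety and medication tables. The primary test is not shown to change.

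**What to change.** Amend SAP 4.5, with matching references in 7.2 and 9.1.1, before unblinding:

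- Apply the missing-day rule at interim and final analyses alike, together with the bounds below. Extending it alone would carry the problem in step 2 to the final analysis.
- Set an imputed AE onset no earlier than first dose when the known date parts and the end date allow it. Count an onset set to the first-dose date as treatment-emergent, since 9.1.1 asks for onset after first dose.
- Set an imputed stop date no earlier than the start of the same record and no later than death, last contact or the data cut.
- State that for year-only AE onsets the on-study and treatment-emergent default takes precedence over the 15 July rule.
- State that adjudicated event dates are not imputed under 4.5.

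The cost is SAP wording and a few lines of derivation code.
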